To ensure maintenance of the study blind in the ongoing ISIS 420915-CS2 study, TTR, RBP4, retinol, and NT-proBNP from the first 13 weeks of treatment in this study will not be available to the Sponsor, Investigators, Study Center Personnel, or the patients until the ISIS 420915-CS2 study is unblinded.

The mNIS+7 assessment will be conducted at Weeks 26, 52, 78, 104, 130, and 156. The NIS assessment will be conducted at Y4-W52 and Y5-W52. The Norfolk QOL-DN questionnaire is conducted at Weeks 26, 52, 78, 104, 130, 156, and Y4-W52 and Y5-W52. The Norfolk QOL-DN questionnaire should be the first assessment performed at these visits. If ISIS 420915 administration, ERG, or ophthalmology examinations are to be performed on the same day as an mNIS+7 or NIS assessment, they should be performed after the mNIS+7 or NIS assessment is complete. For Week 78 and Week 156 visits, 2 mNIS+7 assessments will be performed on separate days. A maximum of 2 weeks from the visit (Week 78 or Week 156) will be allowed to complete both assessments.

For Weeks 4-52 there is a \pm 7-day visit window. After Week 52 the visit window is \pm 10-day. All reasonable attempts should be made to ensure compliance with the visit schedule as outlined in the schedule of procedures (Appendix A). However, if a visit does not occur or is delayed, all subsequent visits should be calculated based on the time elapsed since Day 1 rather than from the date of the previous visit.

The Study Day 1 ECHO can be done any time in the screening period or up to 2 weeks after Day 1. The Day 1 ECHO is not done if the Week 65 ECHO was conducted in ISIS 420915-CS2. A \pm 2-week window is given for all other ECHOs.

During the treatment period, an ophthalmology examination will be performed at Weeks 26, 52, 78, 104, 130, 156, and 2 times in each subsequent year (26^{th} and 52^{nd} week of each year). An ERG examination will be performed at Weeks 78 and 156. A window of \pm 2 weeks is allowed for these eye examinations. Early termination ERG and ophthalmology examinations are only done if the patient discontinues treatment after \geq 9 months of dosing or unless deemed necessary by Investigator or Study Medical Monitor.

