14. APPENDICES

Appendix A Schedule of Procedures

Appendix A Schedule of Procedures

	Screen							Y	ear 1							Ye	ar 2			Y	ear3	
		W	W	W	W	W	W	W	W	W	W	W	W	W	W	W	W	W	W	W	W	W
Study Week	s 4 weeks ¹	1	4	7	10	13	15	18	21	23	26	29	39	52	65	78	91	104	117	130	143	156
	0.004.04	D	D	D	D	D	D	D	D	D	D	D	D	D	D	D	D	D	D	D	D	D
Study Day	S-28 to S-1	1	22	43	64	85	99	120	141	155	176	197	267	358	449	540	631	722	813	904	995	1086
Visit Window (+/- Days)		0	7	7	7	7	7	7	7	7	7	7	7	7	10	10	10	10	10	10	10	10
Informed Consent	X																					
Inclusion/Exclusion	X																					
ISIS 420915 Admin. (weekly)2		X	X	X	X	X	X	X	X	X	X	X	X	X	X	X	X	X	X	X	X	X
Safety Assessments																						
Full Physical Exam	хЗ					X					X			X		X		X		X		X
Vital SignsA(BP ⁴ , HR, RR, temp)	х3	X		X		X					X			X		X		X		X		X
ECGA(12-Lead, triplicate)	хЗ										X			X		X		X		X		X
ERG Exams																X						X
Ophthalmology Exams											X			X		X		X		X		X
AE & Con Meds & Concomitant procedures	X	X	X	X	X	X	X	X	X	X	X	X	X	X	X	X	X	X	X	X	X	X
Phone Contact ⁶			X		X		X	X	X	X		X	X		X		X		X		X	

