- Visit based safety assessments (scheduled and unscheduled) will be assigned to a visit according to analysis visit windows in the table 3 of Appendix 3 Analysis Visit Windows, even if they occurred within one of the visit windows. Except for platelet assessments from the local laboratory, local laboratory assessment will not be assigned to a visit and the nominal visit only will be presented in the listings. Safety assessments that occurred during the safety post-treatment period (i.e., more than 7 days after the last dose of study drug) will not be included in

the visit based safety analyses during the safety treatment period. If there are multiple visits within a window, the visit nearest the target day will be used unless two visits are equally near, in which case the average will be used. Note that safety assessments that are not utilized in the visit based summary tables will appear in listings and be used in the determination of treatment-emergent shifts or abnormalities.

• To assess the impact of treatment discontinuation on safety parameters, data from visit based safety assessment in the post treatment phase may also be summarized with respect to the elapsed time from last dose. Assessment will be slotted into follow-up visit windows according to elapsed time from last dose based on the scheduled assessments during the post-treatment evaluation period of the study. The planned windows for this investigation are shown in the table 4 of Appendix 3 Analysis Visit Windows.

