Safety Endpoints: ERG and ophthalmology examinations	-Listings -On-treatment summary tables (CS3) -Post-treatment summary tables	-On-treatment (CS3 period): CS3 Study Day ls Date of assessment 5 Last dose date+ 28 days -Post-treatment: Date of assessment> last dose date+ 28 days -Visit defined by analysis visit window
Safety Endpoints: abnormal lab, worst ECG, meeting Stopping rule	-Listings -On-study summary tables (CS3)	-Abnormal lab analyses described in Sections 3.3.4.1 to 3.3.4.3 include post-baseline data collected from CS3 Study Day 1 up to the day of the patient's last contact date within the study
Safety Endpoints: AE	-Listings -On-treatment (CS3) summary tables -On-study (CS3) summary tables	-On-treatment: CS3 Study Day ls Date of assessment 5 Last dose date + 7 days -On-study summary tables includes all treatment emergent adverse event (TEAE) in the OLE study, including those with onset dates> last dose date + 7 days
Selected Safety Endpoints: abnormal lab and AEs	- Longitudinal safety summary for overall parent study and OLEstudy	- Longitudinal safety summary for overall parent study and OLE study include data collected from the first dose of ISIS 420915 in the parent study and ends on the day of the patient's last contact date within the study, (1) for subjects who enrolled in the OLE study, it is the last contact date within the OLE study; (2) for subjects who are not enrolled in the OLE study but had been administered ISIS 420915 in the parent study, it is the last contact date within the parent study.
Concomitant medications	-Listings -On-treatment (CS3) summary tables -On-study (CS3) summary table	-On-treatment: CS3 Study Day ls Date of assessment s Last dose date + 7 days -On-study summary tables includes all concomitant medication in the OLE study, including those with onset dates > last dose date+ 7 days
Immunogenicity	-Listings -On-study (CS2 and CS3)	-On-study summary/analysis tables include data collected from the CS2 Study Day 1 up to the day of the

Endpoint type	Output type	Comment/definition
	summary/ analysis tables	patient's last contact date within the study (showing both CS2 visits and CS3 visits) -Visit defined by analysis visit window.
PK	-Listings -On-study (CS3) summary/ analysis tables	-Summary/analysis tablesinclude data collected from CS3 Study Day 1 up to the day of the patient's last contact date within the study -PK concentration will be summarized based onnominal scheduled visits (showing CS3 visits)

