8.3 Appendix 3 Analysis Visit Windows and Follow-Up Visit Window

8.3.1 Table 1. Efficacy Endpoints and PD Endpoints (On-Treatment Analysis Visit Wondow):

Visit window for mNIS+7 and individual components:

	Nominal Visit (Target Day)	Analysis Visit Window (Day)
the Parent study	Week 35 (Day 239)	209-269
	Week 66 (Day 456)	411-501
The OLE study	Week 26 (Day 176)	146 - 206
	Week 52 (Day 358)	328 - 388
	Week 78 (Day 540)	510 - 570
	Week 104 (Day 722)	692 - 752
	Week 130 (Day 904)	874 - 934
	Week 156 (Day 1086)	1041-1131

Visit window for NIS and individual components, NSC, Norfolk QOL-DN and individual components:

	Nominal Visit (Target Day)	Analysis Visit Window (Day)
the Parent	Week 35 (Day 239)	209-269
study		
	Week 66 (Day 456)	411-501
The OLE study	Week 26 (Day 176)	146 - 206
	Week 52 (Day 358)	328 - 388
	Week 78 (Day 540)	510 - 570
	Week 104 (Day 722)	692 - 752
	Week 130 (Day 904)	874 - 934
	Week 156 (Day 1086)	1041-1131
	Y4-W52 (Day 1450)	1420 - 1480
	Y5-W52 (Day 1814)	1784 - 1844

Visit window for SF-36 Questionnaire and PND Score:

	Nominal Visit (Target Day)	Analysis Visit Window (Day)
the Parent study	Week 35 (Day 240)	210-270
	Week 65 (Day 449)	397-501
The OLE study	Week 26 (Day 176)	146 - 206
	Week 52 (Day 358)	328 - 388
	Week 78 (Day 540)	510 - 570

Nominal Visit (Target Day)	Analysis Visit Window (Day)
Week 104 (Day 722)	692 - 752
Week 130 (Day 904)	874 - 934
Week 156 (Day 1086)	1041 - 1131
Y4-W52 (Day 1450)	1420 - 1480
Y5-W52 (Day 1814)	1784 - 1844

Visit window for Body Weight, BMI and mBMI:

	Nominal Visit (Target Day)	Analysis Visit Window (Day)
the Parent	Week 13 (Day 85)	55-115
study		
	Week 35 (Day 240)	210-270
	Week 53 (Day 365)	335-395
	Week 65 (Day 449)	419-479
The OLE study	Week 13 (Day 85)	55-115
	Week 26 (Day 176)	146-206
	Week 52 (Day 358)	328-388
	Week 78 (Day 540)	510-570
	Week 104 (Day 722)	692-752
	Week 130 (Day 904)	874-934
	Week 156 (Day 1086)	1056-1116

Visit window for PD Panel (TTR and RBP4):

	Nominal Visit (Target Day)	Analysis Visit Window (Day)
the Parent study	Week 3 (Day 15)	2-21
	Week 5 (Day 29)	22-38
	Week 8 (Day 50)	39-66
	Week 13 (Day 85)	67-101
	Week 18 (Day 120)	102-136
	Week 23 (Day 155)	137-175
	Week 29 (Day 197)	176-217
	Week 35 (Day 240)	218-259
	Week 41 (Day 281)	260-301
	Week 47 (Day 323)	302343
	Week 53 (Day 365)	344-385
	Week 59 (Day 407)	386-427
	Week 65 (Day 449)	428-469

	Nominal Visit (Target Day)	Analysis Visit Window (Day)
The OLE study	Week 7 (Day 43)	13-63

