	Week 52 (Day 358)	328-388
	Week 78 (Day 540)	510-570
	Week 104 (Day 722)	629-752
	Week 130 (Day 904)	874-934
	Week 156 (Day 1086)	1056-1116

ECG

Safety endpoint	Nominal Visit (Target Day)	Analysis Visit Window (Day)	
The OLE study	Week 26 (Day 176)	146-206	
	Week 52 (Day 358)	328-388	
	Week 78 (Day 540)	510-570	
	Week 104 (Day 722)	629-752	
	Week 130 (Day 904)	874-934	
	Week 156 (Day 1086)	1056-1116	
	Y4-W26 (Day 1268)	1238-1298	
	Y4-W52 (Day 1450)	1420-1480	
	Y5-W26 (Day 1632)	1602-1662	

Safety endpoint	Nominal Visit (Target Day)	Analysis Visit Window (Day)
	Y5-W52 (Day 1814)	1784-1844

Chemistry Panel, Hematology and Urinalysis

Safety endpoint	Nominal Visit (Target Day)	Analysis Visit Window (Day)
The OLE study	Week 4 (Day 22)	11-31
	Week 7 (Day 43)	32-52
	Week 10 (Day 64)	53-73
	Week 13 (Day 85)	74-91
	Week 15 (Day 99)	92-108
	Week 18 (Day 120)	109-129
	Week 21 (Day 141)	130-147
	Week 23 (Day 155)	148-164
	Week 26 (Day 176)	165-185
	Week 29 (Day 197)	186-227
	Week 39 (Day 267)	237-297
	Week 52 (Day 358)	328-388
	Week 65 (Day 449)	419-479
	Week 78 (Day 540)	510-570
	Week 91 (Day 631)	601-661
	Week 104 (Day 722)	692-752
	Week 117 (Day 813)	783-843
	Week 130 (Day 904)	874-934
	Week 143 (Day [contact]
	Week 156 (Day 1086)	1056-1116
	Y4-W13 (Day 1177)	1147-1207
	Y4-W26 (Day 1268)	1238-1298
	Y4-W39 (Day 1359)	1329-1389
	Y4-W52 (Day 1450)	1420-1480
	Y5-W13 (Day 1541)	1511-1571
_	Y5-W26 (Day 1632)	1602-1662
	Y5-W39 (Day 1723)	1693-1753
	Y5-W52 (Day 1814)	1784-1844

Serum Creatinine

Safety endpoint	Nominal Visit (Target Day)	Analysis Visit Window (Day)
The OLE study	Week 4 (Day 22)	11-31
	Week 7 (Day 43)	32-52

Safety endpoint	Nominal Visit (Target Day)	Analysis Visit Window (Day)
	Week 10 (Day 64)	53-73
	Week 13 (Day 85)	74-91
	Week 15 (Day 99)	92-108
	Week 18 (Day 120)	109-129
	Week 21 (Day 141)	130-147
	Week 23 (Day 155)	148-164
	Week 26 (Day 176)	165-185
	Week 29 (Day 197)	186-203
	Week 31 (Day 211)	204-217
	Week 33 (Day 225)	218-231
	Week 35 (Day 239)	232-245
	Week 37 (Day 253)	246-259
	Week 39 (Day 267)	260-273
	Week 41 (Day 281)	274-287
	Week 43 (Day 295)	288-301
	Week 45 (Day 309)	302-315
	Week 47 (Day 323)	316-329
	Week 49 (Day 337)	330-346
	Week 52 (Day 358)	347-364
	Week 54 (Day 372)	365-378
	Week 56 (Day 386)	379-392
	Week 58 (Day 400)	393-406
	Week 60 (Day 414)	407-420
	Week 62 (Day 428)	421-437
	Week 65 (Day 449)	438-455
	Week 67 (Day 463)	456-469
	Week 69 (Day 477)	470-483
	Week 71 (Day 491)	484-497
	Week 73 (Day 505)	498-511

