	Y5-W36 (Day 1702)	1698-1704
	Y5-W37 (Day 1709)	1705-1711
	Y5-W38 (Day 1716)	1712-1718
	Y5-W39 (Day 1723)	1719-1725
	Y5-W40 (Day 1730)	1726-1732
	Y5-W41 (Day 1737)	1733-1739
	Y5-W42 (Day 1744)	1740-1746
	Y5-W43 (Day 1751)	1747-1753
	Y5-W44 (Day 1758)	1754-1760
	Y5-W45 (Day 1765)	1761-1767
	Y5-W46 (Day 1772)	1768-1774
	Y5-W47 (Day 1779)	1775-1781
	Y5-W48 (Day 1786)	1782-1788
	Y5-W49 (Day 1793)	1789-1795
	Y5-W50 (Day 1800)	1796-1802
	Y5-W51 (Day 1807)	1803-1809
	Y5-W52 (Day 1814)	1810-1816

Thyroid Panel and Coagulation: PT, aPTT, INR

Safety endpoint	Nominal Visit (Target Day)	Analysis Visit Window (Day)	
The OLE study	Week 7 (Day 43)	13-63	
	Week 13 (Day 85)	64-115	
	Week 26 (Day 176)	146-206	
	Week 52 (Day 358)	328-388	
	Week 78 (Day 540)	510-570	
	Week 104 (Day 722)	629-752	
	Week 156 (Day 1086)	1056-1116	
	Y4-W26 (Day 1268)	1238-1298	
	Y4-W52 (Day 1450)	1420-1480	
	Y5-W52 (Day 1814)	1784-1844	

 $^{^{\}dagger}\text{ISIS}\,420915$ baseline for patients took placebo in the parent study.

Immunogenicity

Safety endpoint	Nominal Visit (Target Day)	Analysis Visit Window (Day)
The OLE study	Week 7 (Day 43)	13-63
	Week 13 (Day 85)	64-101
	Week 18 (Day 120)	102-147
	Week 26 (Day 176)	148-206
	Week 39 (Day 267)	237-297
	Week 52 (Day 358)	328-388
	Week 65(Day 449)	419-479
	Week 78 (Day 540)	510-570
	Week 91 (Day 631)	601-661
	Week 104 (Day 722)	692-752
	Week 117 (Day 813)	783-843
	Week 130 (Day 904)	874-934
	Week 143 (Day [contact]
	Week 156 (Day 1086)	1056-1116
	Y4-W52 (Day 1450)	1420-1480
	Y5-W52 (Day 1814)	1784-1844

ERG

Safety endpoint	Nominal Visit (Target Day)	Analysis Visit Window (Day)
The OLE study	Week 78 (Day 540)	510-570
	Week 156 (Day 1086)	1056-1116

Ophthalmology

Safety endpoint	Nominal Visit (Target	Analysis Visit Window (Day)
	Day)	
The OLE study	Week 26 (Day 176)	146-206
	Week 52 (Day 358)	328-388
	Week 78 (Day 540)	510-570
	Week 104 (Day 772)	742-802
	Week 130 (Day 904)	874-934
	Week 156 (Day 1086)	1056-1116
	Y4-W26 (Day 1268)	1238-1298
	Y4-W52 (Day 1450)	1420-1480
	Y5-W26 (Day 1632)	1602-1662
	Y5-W52 (Day 1814)	1784-1844

Inflammatory Panel: Hs-CRP

Safety endpoint	Nominal Visit (Target Day)	Analysis Visit Window (Day)	
The OLE study	Week 7 (Day 43)	22-63	
	Week 13 (Day 85)	64-115	
	Week 26 (Day 176)	146-206	
	Week 52 (Day 358)	328-388	
	Week 78 (Day 540)	510-570	
	Week 91 (Day 631)	601-661	
	Week 104 (Day 722)	692-752	
	Week 117 (Day 813)	783-843	
	Week 130 (Day 904)	874-934	
	Week 143 (Day [contact]	

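### Five Week 104 rows in SAP Appendix 3 Table 3 are wrong: the ophthalmology window contains no on-schedule exam day, and four other safety windows open 63 days early

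*Combined protocol and SAP*

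**What the plan says.** SAP 3.2.1.3 assigns scheduled and unscheduled safety assessments to visits using the windows in Appendix 3 Table 3. When a window holds several results, "the visit nearest the target day will be used unless two visits are equally near"; ties are averaged.

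The Week 104 rows at issue in Table 3 are:

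- **Ophthalmology:** "Week 104 (Day 772", window 742-802.
- **Vital signs with retinol and retinyl palmitate; body weight; ECG; thyroid and coagulation:** target Day 722, window 629-752 in all four tables.

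Elsewhere in Appendix 3, the Table 3 section headed "Chemistry Panel, Hematology and Urinalysis" gives 692-752 for Week 104, as do the immunogenicity and hs-CRP tables. In Table 1, the section headed "Visit window for Body Weight, BMI and mBMI" also gives 692-752, as do the mNIS+7, NIS/Norfolk, SF-36/PND, PD and NT-proBNP tables.

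Protocol Appendix A places Week 104 at Study Day 722 and marks an exam in the "Ophthalmology Exams" row at that visit. Protocol 6.1.2 states that a margin of two weeks either side "is allowed for these eye examinations".

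SAP 3.2.1.4 has a row for "Safety Endpoints: ERG and ophthalmology examinations" that foresees on-treatment summary tables with visits defined by analysis window. SAP 3.3.6 says only that ophthalmology findings are listed, with a count of patients reaching the ocular stopping rule.

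**The concern.** The windows decide which result appears under which visit. A window that misses the scheduled day leaves compliant data without a visit. A window that opens too early can put a result under a visit label to which it does not belong.

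Both seem to happen at Week 104. The ophthalmology target is 50 days later than the protocol's day. The other four windows reach 93 days before target but only 30 after. Body weight has two different Week 104 windows in the same appendix, so the SAP disagrees with itself without reference to any outside standard.

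Safety and tolerability is the primary objective, and ocular events related to vitamin A deficiency are an adverse event of special interest. At stake is whether the by-visit safety tables show the right patients at Week 104.

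**Working it through.** **Inputs.** Week 104 = Day 722, visit window ±10 days (Protocol Appendix A); eye exams ±14 days (Protocol 6.1.2); all analysis windows from SAP Appendix 3.

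**Target day.** Study day = 1 + 7 × (week − 1). This gives 176, 358, 540, 904 and 1086 for Weeks 26, 52, 78, 130 and 156, matching the ophthalmology rows. For Week 104 it gives 1 + 7 × 103 = 722, not 772.

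**Reproducing the printed ophthalmology window.** 772 − 30 = 742 and 772 + 30 = 802, so the window follows from the printed target. The other nine ophthalmology rows are also exactly target ±30. The same pattern at Day 722 gives 692-752.

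**Compliant exam days against the ophthalmology windows.**
- Allowed days: 722 ± 14 = 708-736, which is 736 − 708 + 1 = 29 days.
- Overlap with 742-802: 0 days. The neighbouring windows are 510-570 (Week 78) and 874-934 (Week 130), and their overlap is also 0.
- The printed window shares 752 − 742 + 1 = 11 days with 692-752. Its other 802 − 753 + 1 = 50 days lie 753 − 722 = 31 to 802 − 722 = 80 days after the correct target.

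**The four 629-752 windows.**
- Reach: 722 − 629 = 93 days before target; 752 − 722 = 30 days after.
- Width: 752 − 629 + 1 = 124 days, against 752 − 692 + 1 = 61. Excess: 124 − 61 = 63 days (Days 629-691).
- On-schedule days: 722 ± 10 = 712-732, 21 days, all inside 629-752.

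**Where same-day results go on Days 629-691.**

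| Days | Number of days | The four tables | Chemistry | BMI (Table 1) |
|---|---|---|---|---|
| 629-661 | 661 − 629 + 1 = 33 | Week 104 | Week 91 (601-661) | no visit |
| 662-691 | 691 − 662 + 1 = 30 | Week 104 | no visit | no visit |

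The two rows sum to 63 days. BMI has no window between 570 and 692, so it is unassigned on all 63.

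**Rows left out of the comparison.** Serum creatinine (711-728) and platelets (718-724) are sampled more often, have narrower windows to match, and contain Day 722. Five Week 104 rows in Table 3 are therefore anomalous.

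**The case against.** The strongest counter-argument is that little or no specified output changes.

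- **Ophthalmology.** SAP 3.2.1.4 has one joint row for ERG and eye exams and allows exceptions noted elsewhere. SAP 3.3.6 summarizes ERG change but only lists eye findings. The output lists for the interim analyses in SAP 5.1 and 5.2 name ERG by visit and not ophthalmology, and SAP 9.2.1 adds no eye summary. This stands in part: no ophthalmology by-visit statistic is defined beyond the general row. But that row does foresee such tables, SAP 9.1 does not remove them, and Table 3 supplies windows for the purpose. The printed row is wrong whether or not the table is produced.
- **The other four tables.** The nearest-to-target rule protects any patient with an on-schedule result, and all these summaries are descriptive. This stands, and it limits the effect to patients whose only on-treatment result in the window falls on Days 629-691. The protocol schedules none of these assessments then, so such a result would be unscheduled, from early termination, or from a badly displaced Week 78 or Week 104 visit.
- **No stated rule.** The SAP never states ±30 days in words, and some other windows are wider or asymmetric. So 692 as the intended lower bound is an inference from the sister tables, though the duplicate body weight window makes it a strong one. The ophthalmology error needs no such inference, because it contradicts the protocol's Day 722.
- **Stacked margins.** Adding the ±10-day visit window to the ±14-day exam margin gives 698-746, of which 742-746 (5 of 49 days) would be caught. The protocol does not say to add them, and 44 days would still miss.
- **Count differences between tables.** Counts can differ anyway because window widths and on-treatment cut-offs differ. That is true, but it does not justify a further, unintended source of disagreement.

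**Conclusion.** The concern holds. Applied as printed, the ophthalmology row leaves every on-schedule Week 104 eye exam (0 of 29 permitted days captured) without an analysis visit. The four 629-752 rows admit 63 extra days and can label as Week 104 a lone result obtained 31 to 93 days before target.

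The consequences are narrow. SAP 3.2.1.3 provides that "safety assessments that are not utilized in the visit based summary tables will appear in listings", and such data still count towards treatment-emergent shifts and abnormalities. Adverse event, worst-value and stopping-rule outputs do not depend on these windows. No hypothesis test is involved.

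The conclusion assumes that the printed values are the ones programmed, which the documents do not show, and that the four wide windows were meant to match their sister tables. Digit slips (772 for 722, 629 for 692) are the likely cause, but that is inference. How many patients are affected cannot be derived from the documents. The rows should be corrected, but they do not threaten the study's safety conclusions.

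**What to change.** In SAP Appendix 3 Table 3:

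1. Ophthalmology, Week 104: target Day 722, window 692-752. This contains all of Days 708-736.
2. Vital signs/retinol/retinyl palmitate, body weight, ECG, and thyroid/coagulation, Week 104: window 692-752.
3. Compare the programmed windows with the corrected table, and rerun only those by-visit outputs that used the printed values.
4. While editing, state whether an ophthalmology by-visit summary is intended, so that SAP 3.2.1.4 and 3.3.6 agree.

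The cost is five row edits, a clarifying sentence and a program check, plus limited reruns if the wrong values were used. No data collection changes.

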9.1 Analyses Removed from Final Analyses

Per protocol set (PPS) flag will not created in final ADaM dataset and Efficacy and PD analysis based on PPS will not be performed.

Efficacy analysese by subgroup will not be performed.

The degree of progression for mNIS+7 and Norfolk (specified in section 3.4.2.1) will not be performed

The proportion of patients with percentage decrease from either the parent study baseline or the OLE study baseline in plasma transthyretin (TTR) \geq 60% (specified in section 3.5) will not be performed.

9.2 Additional Analyses added for Final Analyses

9.2.1 Based on OLE data only

- Summary of disposition and protocol deviation associated with COVID-19 based on CS3
 Enrolled Patients
- Summary of ISIS 420915 Trough Plasma Concentrations (On-Study) based on safety set.
- Summary of Complement Results (Complement C3, Complement C4, Complement Split Bb, Complement Split C5a) by visit based on safety set
- Summary of TEAE by System Organ Class and Preferred Term and by PND score (On-Study)
 based on safety set
- Lab shift table for Hematology (Hemoglobin, Lymphocyte, Neutrophil, White Blood Cell), Chemistry Test, Coagulation Test, Urinalysis test, Urinalysis Results from Central Lab Based on 24-hr Urine Collections, Confirmed Peak ALT, Confirmed Peak AST, Confirmed Peak Total Bilirubin (On-study) based on safety set.
- Incidence of Post-baseline abnormality, including lab Complement Results, vital signs and body weight and QTcF.

Efficacacy endpoints

On-treatment: Add Statistical Analysis of Change from CS2 Baseline to efficacy endpoints:

mNIS+7, NIS+7, NIS, Modified +7, +7, NSC composite and component score, mNIS+7 composite score, Norfolk QOL-DN, NSC total and domain score and selected questions, SF-36 component and Domain Scores. Norfolk QOL-DN Symptoms Domain Score based on Stage 1 Patients, Norfolk QOL-DN Physical Functioning/Large Fiber Neuropathy Domain Score based on Stage 2 Patients

Post-treatment:

Show Descriptive statistics of absolute value, change from baseline and percent change from baseline in mNIS+7, NIS+7, NIS, Modified +7, +7 Composite and Component, Norfolk QOL-DN Total and Domain Scores, SF-36 Scores, NSC score and Select Questions from NSC

